Week 4 Day 1	22Jan2016 / 22Jan2016	Induction	175 weekly	175	No	No		
Week 7 Day 1	13Feb2016 / 13Feb 2016	Induction	175 weekly	175	No	No		
Week 8 Day 1	20Feb2016 / 20Feb2016	Induction	175 weekly	175	No	No		
Week 9 Day 1	28Feb2016 / 28Feb2016	Induction	175 weekly	175	No	No		
Week 10 Day 1	09Mar2016 / 09Mar 2016	Induction	175 weekly	175	No	No		
Week 13 Day 1	31Mar2016 / 31Mar2016	Maintenance C1	175 weekly	175	No	No		
Week 14 Day 1	08Apr2016 / 08Apr 2016	Maintenance C1	175 weekly	175	No	No		
Week 15 Day 1	15Apr2016 / 15Apr2016	Maintenance C1	175 weekly	175	No	No		
Week 16 Day 1	22Apr2016 / 22Apr2016	Maintenance C1	175 weekly	175	No	No		
Week 19 Day 1	14May2016 /14May2016	Maintenance C2	175 weekly	175	No	No		
Week 20 Day 1	21May2016 /21May2016	Maintenance C2	175 weekly	175	No	No		
Week 21 Day 1	28May2016 /28May2016	Maintenance C2	175 weekly	175	No	No		
Week 22 Day 1	04Jun2016 / 04Jun2016	Maintenance C2	175 weekly	175	No	No		

Table 2-10	Examples of carboplatin dose administration and exposur
	Examples of carboplatin uose auministration and exposur

Induction:

Duration of induction = [31Mar2016-1 = 30Mar2016] – 01Jan2016 + 1 = 90 days = 12.86 weeks

Planned dose intensity 116.67 mg/m2/week

Actual cumulative dose induction= 175*6 + 150*1 = 1200 mg/m2

Dose intensity induction = 1200 mg/m2 / 12.86 weeks = 93.3 mg/m2/week

Relative dose intensity induction = DI / PDI = (93.3 mg/m2/week) / (116.67 mg/m2/week) = 80%

Novartis	
SAP Final CSR LGG	

Confidential

Reason

AE AE

AE

Maintenance:

Duration of maintenance = [14May2016 + 41 = 24Jun2016] - 31Mar2016 + 1 = 86 days = 12.29 weeks

Planned dose intensity 116.67 mg/m2/week

Actual cumulative dose maintenance = 175*8 = 1400 mg/m2

09Mar2016 / 09Mar 2016

31Mar2016 / 31Mar2016

08Apr2016 / 08Apr 2016

15Apr2016 / 15Apr2016

Dose intensity maintenance= 1400 mg/m2 / 12.29 weeks = 113.9 mg/m2/week

Relative dose intensity maintenance = DI / PDI = (113.9 mg/m2/week) / (116.67 mg/m2/week) = 97.6%

Nominal Visit number	Start/End Date	Phase	Dose Prescribed (mg/m2), frequency	Dose Administered (mg) [total daily]	Dose Changes, Dose Interruption?	Dose Permanently Discontinued
Week 1 Day 1	01Jan2016 / 01Jan2016	Induction	1.5 weekly	1.5	No	No
Week 2 Day 1	08Jan2016 / 08Jan2016	Induction	1.5 weekly	0	Yes	No
Week 3 Day 1	15Jan2016 / 15Jan2016	Induction	1.0 weekly	1.0	Yes	No
Week 4 Day 1	22Jan2016 / 22Jan2016	Induction	1.5 weekly	1.5	No	No
Week 5 Day 1	28Jan2016 / 28Jan2016	Induction	1.5 weekly	1.5	No	No
Week 6 Day 1	04Feb2016 / 04Feb2016	Induction	1.5 weekly	1.5	No	No
Week 7 Day 1	13Feb2016 / 13Feb 2016	Induction	1.5 weekly	1.5	No	No
Week 8 Day 1	20Feb2016 / 20Feb2016	Induction	1.5 weekly	1.5	No	No
Week 9 Day 1	28Feb2016 / 28Feb2016	Induction	1.5 weekly	1.5	No	No

1.5 weekly

1.5 weekly

1.5 weekly

1.5 weekly

1.5

1.5

1.5

0

No

No

No

No

No

No

No

Yes

Table 2-11 Examples of vincristine dose administration and exposure for \ge 12 kg

Induction:

Week 10 Day 1

Week 13 Day 1

Week 14 Day 1

Week 15 Day 1

Duration of induction = [31Mar2016-1 = 30Mar2016] - 01Jan2016 + 1 = 90 days = 12.86 weeks

Induction

Maintenance C1

Maintenance C1

Maintenance C1

Planned dose intensity induction 1.25 mg/m2/week

Actual cumulative dose induction= 1.5*8 + 1.0*1 = 13 mg/m2

Dose intensity induction = 13 mg/m2 / 12.86 weeks = 1.01 mg/m2/week

Relative dose intensity induction = DI / PDI = (1.01 mg/m2/week) / (1.25 mg/m2/week) = 80.9%

Maintenance:

Duration of maintenance = [31Mar2016 + 41 = 11May2016] - 31Mar2016 + 1 = 42 days = 6 weeks

Planned dose intensity maintenance 0.75 mg/m2/week

Actual cumulative dose maintenance = 1.5*2 + 0*1 = 3 mg/m2

Dose intensity maintenance = 3 mg/m2 / 6 weeks = 0.5 mg/m2/week

Relative dose intensity maintenance = DI / PDI = 0.5 mg/m2/week) / (0.75 mg/m2/week) = 66.7%

Dose reductions, interruptions, re-escalations or permanent discontinuations

The number of patients who have dose reductions, permanent discontinuations or interruptions, and the reasons, will be summarized separately for each of the study treatment components. The number of patients who have dose re-escalations will also be summarized.

'Dose interrupted' and 'Dose permanently discontinued' fields from the Dosage Administration Record eCRF pages (DAR) will be used to determine the dose interruptions and permanent discontinuations, respectively. Dose reductions will be derived programmatically using the dosing information as described below.

The corresponding fields 'Reason for dose change/dose interrupted' and 'Reason for permanent discontinuation' will be used to summarize the reasons.

A dose change is either 'change in prescribed dose level' or 'dosing error' where actual dose administered/total daily dose is different from the prescribed dose.

For the purpose of summarizing interruptions and reasons, in case multiple entries for interruption that are entered on consecutive days with different reasons will be counted as separate interruptions. However, if the reason is the same in this block of entries, then it will be counted as one interruption.

Dose Reduction: Only dose change is collected in the eCRF, the number of reductions will therefore be derived programmatically based on the change and the direction of the change. A dose reduction is a dose change where the prescribed dose level is lower than the previous prescribed dose level or where the actual dose administered/total daily dose is lower than the calculated dose amount based on the prescribed dose. Note that any dose change due to dispensing or dosing error will not be considered a dose reduction. Note also that any previous dose interruptions and any previous dosing or dispensing errors should be ignored when considering whether a subsequent dose change counts as a dose reduction, i.e., if the new dose is lower than the dose prior to any dose interruption or any dose or dispensing error this would still constitute a dose reduction.

Missing data: If dose is recorded but regimen is missing or entered as 'none', it is assumed that the investigational drug was taken as per-protocol.

Dose Re-escalation: For patients with a dose reduction, a dose re-escalation is where the prescribed dose level is higher than the previous prescribed dose level or where the actual dose administered/total daily dose is higher than the calculated dose amount based on the prescribed dose. An increase will only be considered a dose re-escalation if the reason for dose change is "as per protocol". Note also that any previous dose interruptions and any previous dosing or dispensing errors should be ignored when considering whether a subsequent dose change counts as a dose re-escalation.

2.4.2 **Prior, concomitant, on study and post therapies**

Prior anti-cancer therapy

The analyses performed for the primary analysis can be referred to for details on prior anticancer therapies.

Novartis	Confidential	Page 30
SAP Final CSR LGG		CDRB436G2201

On study Radiotherapy and Surgery

As on study radiotherapy and surgeries are allowed after centrally confirmed radiologic progression of disease or at least a total of 36 months of treatment plus follow-up, whichever comes first. Surgeries and radiotherapies occurring on study will be listed only.

Post treatment anti-cancer therapy

Anti-neoplastic therapies since discontinuation of study treatment will be listed and summarized by World Health Organization (WHO) Anatomical Therapeutic Chemical (ATC) classification system, PT, overall and by treatment group by means of frequency counts and percentages using FAS. In addition, summaries will include best response to the regimen. Anti-neoplastic medications will be coded using the WHO Drug Dictionary (WHO-DD).

Concomitant medications

Concomitant therapy is defined as all interventions (therapeutic treatments and procedures) other than the study treatment administered to a patient coinciding with the study treatment period. Concomitant therapy include medications (other than study drugs) starting on or after the start date of study treatment or medications starting prior to the start date of study treatment and continuing after the start date of study treatment.

Concomitant medications will be coded using the WHO Drug Reference Listing (DRL) dictionary that employs the ATC classification system and summarized by lowest ATC class and PT using frequency counts and percentages. Surgical and medical procedures will be coded using MedDRA and summarized by SOC and PT. These summaries will include:

- 1. Medications starting on or after the start of study treatment but no later than 30 days after start of last dose of study treatment and
- 2. Medications starting prior to start of study treatment and continuing after the start of study treatment.

Non-drug therapies and procedures starting after the start of study treatment will also be summarized by SOC and PT.

All concomitant therapies will be listed. Any concomitant therapies starting and ending prior to the start of study treatment or starting more than 30 days after the last date of study treatment will be flagged in the listing. The safety set will be used for all concomitant medication tables and listings.

Systemic corticosteroid use (flagged using a pre-specified list from the clinical team) will be listed and summarized by lowest ATC class and PT using frequency count and percentages. The total daily dose of systemic corticosteroids can be calculated from the dose per administration and the dose frequency (see Section 5.3). Any corticosteroid use starting and ending prior to the start of study treatment or starting more than 30 days after the last date of study treatment will be flagged in the listing. Concomitant medications that have the potential to impact some specific analyses (e.g. efficacy or safety analyses) will be identified prior to database lock. Separate summaries of these concomitant medications will be produced using the appropriate analysis set (e.g. FAS for those potentially affecting efficacy. According to the study protocol, treatment with substances which are strong inhibitors, or inducers of CYP3A4/5

Novartis	Confidential	Page 31
SAP Final CSR LGG		CDRB436G2201

and CYP2C8, or antiretrovirals or herbal medicines or other anti-cancer or anti-investigational drugs should be avoided. However, some patients may take these substances during the treatment period so these concomitant medications will be selected via programming and tabulated and listed in the CSR. Treatment with the prohibited substances mentioned above will be identified in the database as protocol deviations.

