Duration of exposure to vincristine overall (days) = (last date of exposure to vincristine as defined in Table 2-7) – (date of first administration of vincristine) + 1.

Induction phase:

Carboplatin is dosed as weekly IV infusions on weeks 1 to 4, and on weeks 7 to 10 followed by 2 weeks of rest in the *induction phase*. Vincristine is dosed as weekly IV bolus infusion for 10 weeks followed by 2 weeks of rest in the *induction phase*. The induction phase refers to the first 12 weeks of dosing (i.e from day of first dose of carboplatin or vincristine until 84 days).

The *last date of exposur* to carboplatin or vincristine in the induction phase is calculated including the rest periods (2 weeks). If subjects continued on to maintenance therapy, the last date of exposure in induction phase is the day before the start of maintenance therapy. If the subject does not continue on to maintenance therapy, the last date of exposure is calculated using the planned cycle duration, i.e. the last date of exposure is the date of first administration (of carboplatin or vincristine) in induction + 83 days. If the subject dies or if the data cutoff date is prior to the calculated date of last exposure, the date will be capped at the date of death or data cutoff.

Maintenance phase:

Maintenance phase will continue for up to a total of 8 cycles, each cycle will be 6 weeks in duration and consists of 4 weekly doses of carboplatin followed by 2 weeks of rest, and three weekly doses of vincristine given concomitantly with the first 3 weeks of carboplatin , followed by three weeks of rest. The maintenance phase refers to the dosing after the first 12 weeks, and will be identified by having at least 9 non-zero doses of Carboplatin, or at least 11 non-zero doses of Vincristine. For Carboplatin/Vincristine, maintenance cycle week1 dates are defined by the following non-zero doses: dose 9/dose 11, dose 13/dose 14, dose 17/dose 17, dose 21/dose 20, dose 25/dose 23, dose 29/dose 26, dose 33/dose 29, and dose 37/dose 32, respectively.

The *last date of exposur* to carboplatin or vincristine in the induction phase is calculated including the rest periods (2 or 3 weeks). The last date of exposure is calculated using the planned cycle duration, i.e. the last date of exposure is the date of last week 1 administration (of carboplatin or vincristine) in maintenance +41 days. If the subject dies or if the data cutoff

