date is prior to the calculated date of last exposure, the date will be capped at the date of death or data cutoff. The *number of cycles* of maintenance therapy will be determined as the following total number of non-zero doses:

- Carboplatin: 1 cycle 9 to 12 doses; 2 cycles 13-16 doses; 3 cycles 17 to 20 doses; 4 cycles 21 to 24 doses; 5 cycles 25 to 28 doses; 6 cycles 29 to 32 doses; 7 cycles 33 to 36 cycles; 8 cycles ≥ 37 doses.
- Vincristine: 1 cycle 11 to 13 doses; 2 cycles 14-16 doses; 3 cycles 17 to 19 doses; 4 cycles 20 to 22 doses; 5 cycles 23 to 25 doses; 6 cycles 26 to 28 doses; 7 cycles 29 to 31 cycles; 8 cycles ≥ 32 doses.

Duration of exposure to carboplatin and vincristine (days) will be calculated by treatment phase (induction and maintenance phase) and overall (if applicable) as:

Duration of [study drug] exposure (days) in induction phase = (Date of first week1 dose of [study drug] in maintenance -1 day) - (date of first administration of [study drug]) + 1, for those who entered maintenance. For those who did not enter maintenance therapy, duration of maintenance will be defined as [minimum (date of first administration of [study drug] + 83 days, date of death, date of data cutoff) - (date of first administration of [study drug]) + 1.

Duration of [study drug] exposure (days) in maintenance phase = [minimum(Date of last week1 dose of [study drug] in maintenance + 41 days, date of death, date of data cutoff)] - (date of first week1 dose of [study drug] in maintenance) + 1.

	Deminion of last date of expectate of study and				
Scenario	Definition of last date of exposure of study drug	Example			
Carboplatin, Vincristine	The planned end date of the last cycle in which the last non-zero dose of the investigational drug was last administered (i.e. last week 1 date of administration + (planned interval duration of either induction or maintenance, as applicable))				
	If carboplatin or vincristine was permanently discontinued during induction, set the last date of exposure equal to the planned end date of induction.	Example 1: Subject discontinues during induction therapy. The last date of exposure is the first date of administration + 83 days.			

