	If carboplatin or vincristine was permanently discontinued during maintenance, set the last date of exposure equal to the planned end date of the last cycle, last week 1 administration date + 41 days.	Example 2: Subject discontinues during maintenance therapy after receiving the week 45 dose. The week 43 (C dose 29/V dose 26) dose date was 21Jan2021. The last date of exposure is the 21Jan2021 + 41 days = 03Mar2021.			
	If carboplatin or vincristine was not permanently discontinued, set the last date of exposure equal to the data cut-off date. Note: If the patient died or was lost to follow-up before the derived last date, the last date of exposure to investigational drug is the date of death or the date of last	Example 3: if carboplatin or vincristine was not permanently discontinued prior to or on the data cut-off date, the last date of exposure is the data cut-off date			

 Table 2-7
 Definition of last date of exposure of study drug

Scenario	Definition of last date of exposure of study drug	Example
	contact, respectively. If the derived last date of exposure goes beyond the data cut-off date, it should be truncated to the date of data cut-off.	
Dabrafenib, Trametinib	Date of last administration of a non-zero dose of the study drug.	Example 4: A patient had a permanent discontinuation of the study drug on 06Jan2016 after being put on a temporary interruption since 01Jan2016. In this case the last date of exposure is 31Dec2015.

Summary of duration of exposure to each combination partner will include categorical summaries based on clinically meaningful time intervals (8-<24, 24-<56, 56-<112, >= 112 (weeks)) and using descriptive statistics (i.e. n, mean, standard deviation, median, 25^{th} - 75^{th} percentiles, minimum, and maximum) using appropriate units of time.

Cumulative dose and average daily dose

Cumulative dose of a study treatment is defined as the total dose given during the study treatment exposure and will be summarized for each of the study treatment component, respectively. Average daily dose is defined as [Cumulative dose (dosing unit) / Number of dosing days]; drug free days are not counted as dosing days.

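### LGG final SAP 2.4.1 finds chemotherapy maintenance by counting non-zero doses, which fails when a dose is omitted and contradicts the SAP's own worked examples

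*SAP*

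**What the plan says.** The LGG final SAP, section 2.4.1, describes maintenance in two ways. It first calls it the dosing that follows the first 12 weeks. It then says the phase "will be identified by having at least 9 non-zero doses of Carboplatin, or at least 11 non-zero doses of Vincristine". Cycle starts use the same count: "maintenance cycle week1 dates are defined by the following non-zero doses: dose 9/dose 11, dose 13/dose 14, dose 17/dose 17", and so on up to dose 37 for carboplatin and dose 32 for vincristine. Cycle totals are read from bands of non-zero doses, ending at "8 cycles ≥ 37 doses" for carboplatin and "8 cycles ≥ 32 doses" for vincristine.

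Maintenance duration ends at "minimum(Date of last week1 dose of [study drug] in maintenance + 41 days, date of death, date of data cutoff". Dose intensity and relative dose intensity (RDI) are reported separately for induction and maintenance.

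Tables 2-10 and 2-11 work through one patient for each drug. Both use "Duration of induction = [31Mar2016-1 = 30Mar2016" as the end of induction, so maintenance starts on 31Mar2016. The carboplatin example ends with "Relative dose intensity maintenance = DI / PDI = (113.9 mg/m2/week) / (116.67 mg/m2/week) = 97.6"%.

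Overall exposure, as distinct from phase duration, takes its last date from Table 2-7. The lead row uses the planned end of the last cycle that contained a non-zero dose. A later row, for a drug not permanently discontinued, says to "set the last date of exposure equal to the data cut-off date".

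**The concern.** A count of non-zero doses stands in for calendar position only while every scheduled dose is given. One omitted induction dose makes the week 13 dose the 8th non-zero carboplatin dose or the 10th non-zero vincristine dose. The rule then leaves that dose in induction, although it falls after the first 12 weeks. A programmer following the text and one following the examples would produce different phase dates, cycle counts and RDI from the same records. Omissions are foreseeable, since both of the SAP's chemotherapy examples contain one. These tables are where a reader looks to see how fully the randomized comparator was delivered.

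A second, conditional problem is that Table 2-7 has no row for a patient who finishes the fixed course. If such a patient is treated as not permanently discontinued, the cut-off row applies, which conflicts with the table's lead row and with the rule in the text (last cycle week 1 plus 41 days).

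**Working it through.** **Inputs.** Dose dates and amounts: Tables 2-10 and 2-11. Planned dose intensity (PDI): carboplatin 116.67 mg/m²/week; vincristine 1.25 (induction) and 0.75 (maintenance) mg/m²/week. RDI = [cumulative dose ÷ (days ÷ 7)] ÷ PDI. Maintenance ends at the last cycle week 1 date plus 41 days.

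**Step 1: reproduce the examples (maintenance from 31Mar2016).**
- Carboplatin induction: 90 days, 175×6 + 150 = 1200; 1200/12.86 = 93.3; RDI 80.0%.
- Carboplatin maintenance: to 14May + 41 = 24Jun2016, 86 days, 175×8 = 1400; 1400/12.29 = 113.9; RDI 97.6% (97.7% if weeks are not rounded).
- Vincristine induction: 90 days, 1.5×8 + 1.0 = 13; 13/12.86 = 1.01; RDI 80.9%.
- Vincristine maintenance: 42 days, 3 mg/m²; 3/6 = 0.5; RDI 66.7%.

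All four agree with the SAP.

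**Step 2: apply the written rule to the same rows.** With week 2 at zero, the carboplatin patient has 7 non-zero induction doses, so 31Mar2016 is dose 8 and 08Apr2016 is dose 9. The vincristine patient has 9, so 31Mar2016 is dose 10 and 08Apr2016 is dose 11. Carboplatin cycle 2 starts at dose 13, which is 21May2016; the example uses 14May2016, dose 12.
- Carboplatin induction: 98 days = 14 weeks, 1200 + 175 = 1375; 98.2; RDI 84.2%.
- Carboplatin maintenance: 08Apr to 21May + 41 = 01Jul2016, 85 days = 12.14 weeks, 1400 − 175 = 1225; 100.9; RDI 86.5%.
- Vincristine induction: 14 weeks, 13 + 1.5 = 14.5; 1.036; RDI 82.9%.
- Vincristine maintenance: 42 days, 1.5; 0.25; RDI 33.3%.

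| | Example | Written rule |
|---|---|---|
| Maintenance start | 31Mar2016 | 08Apr2016 |
| Carboplatin RDI, induction / maintenance | 80% / 97.6% | 84.2% / 86.5% |
| Vincristine RDI, induction / maintenance | 80.9% / 66.7% | 82.9% / 33.3% |

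Both maintenance values move to a lower RDI category in the SAP's scheme (cut points 50, 75, 90 and 110%). The induction values stay in theirs. 31Mar2016 is day 91, so the examples agree with the SAP's 12-week (84-day) definition of induction and the count does not.

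**Step 3: cycle counts.** Planned doses are 8 + 8×4 = 40 for carboplatin and 10 + 8×3 = 34 for vincristine. Eight cycles require at least 37 and 32. A patient who passes through all eight but misses 4 carboplatin doses (36 left) or 3 vincristine doses (31 left) is counted as seven. A patient with one omitted induction dose who stops after the first maintenance dose (8 carboplatin or 10 vincristine doses) is counted as never entering maintenance. The two examples keep their own counts (15 doses give 2 cycles; 11 doses give 1).

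**Step 4: size over a full course** (assumed: exact weekly spacing, eight cycles, full dose when given).
- One omitted induction dose. Carboplatin maintenance: 31×175/48 = 113.0, RDI 96.9% against 100%. Vincristine maintenance: 23×1.5/48 = 0.719, RDI 95.8% against 100%. Carboplatin induction: 8×175/13 = 107.7, RDI 92.3% against 7×175/12 = 102.1, RDI 87.5%; this crosses the 90% cut point.
- Four omitted carboplatin induction doses. Rule: 28×175/42 = 116.67, RDI 100%, the same as by scheduled week; cycles fall to 7.

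**Step 5: Table 2-7 cut-off row.** The planned course is 12 + 8×6 = 60 weeks. The final cut-off is at least 2 years after the last patient's first treatment: 2×365.25/7 = 104.4 weeks. If the cut-off row applied to a completer still in follow-up, the excess would be at least 104.4 − 60 = about 44 weeks.

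**The case against.** The strongest reply is that little hangs on this. The final analysis is descriptive, and ORR, PFS and OS do not use these variables. Total cumulative dose, interruption and reduction counts and the listings of every dose do not depend on phase, so delivery of the comparator can still be judged. The intent can be recovered from the 12-week definition and the examples. Doses that are delayed but not omitted do not upset the count. All of that stands, and it limits the severity. It does not remove a rule that the SAP's own examples break.

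Four stronger readings are tempting and not supported:
- A reader might take the example shifts, such as 66.7% to 33.3%, as typical. They arise because the examples cover two carboplatin cycles and two given vincristine maintenance doses.
- A reader might infer that omissions always lower maintenance RDI. Four omitted carboplatin induction doses leave it at 100% under either method.
- A reader might see Table 2-10 as contradicting Table 2-7, since no row records permanent discontinuation and yet the calculation stops at 24Jun2016. That date is a phase end under the phase formula. Table 2-7 feeds overall exposure, which the example never calculates.
- A reader might conclude that completers are certain to be given exposure up to cut-off. The SAP does not say how completing eight cycles is coded, and Table 2-7's lead row gives a sensible date for them.

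**Conclusion.** Wrong as written, of moderate severity. The dose-count rule contradicts both chemotherapy examples and the SAP's 12-week definition; this needs no assumption beyond the printed rows. On those rows maintenance starts 8 days late and RDI changes as tabulated. Over a full course the RDI differences would usually be smaller, though a category can still change. Cycle counts are understated after 4 missed carboplatin or 3 missed vincristine doses. The effect is confined to descriptive control-arm exposure.

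The Table 2-7 point is conditional. If completion is not coded as permanent discontinuation, overall exposure for completers would run at least about 44 weeks too long. Phase-wise dose intensity and RDI would not be touched, because they use the phase formula.

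**What to change.** In section 2.4.1, assign phase and cycle by scheduled dose or nominal week, counting zero-dose records. Carboplatin's 9th and 13th scheduled records and vincristine's 11th then fall on weeks 13, 19 and 13, which is what the examples use. Derive cycle week 1 dates, cycle counts, phase durations and RDI from that assignment. Count a cycle as started only if it contains a non-zero dose, in line with Table 2-7's lead row.

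In Table 2-7, state that patients who complete treatment use the planned end of the last started cycle, and that data cut-off acts only as a cap.

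The cost is a few lines of SAP text and reprogramming of the control-arm exposure variables. It assumes that omitted doses appear as dated zero-dose records or that the nominal visit is held in the data. The example tables show both, but the SAP does not say they are collected fields, so this should be confirmed first. LGG SAP Amendment 1 (2021) carries the same rule and examples, so exposure tables produced under it should be checked for which version was programmed.
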